8.5.1 Extent of exposure

The following dose exposure variables will be derived and summarized for each treatment (BNT411 in Part 1A also BNT411, atezolizumab, carboplatin, and etoposide in Part 1B). The summaries will be based on patients in the Safety set and will be repeated for DLT evaluation set. The summary for the DLT evaluation set will be restricted to the exposure data from the first cycle (21 days).

- Number of treated cycles.
- Number of BNT411 infusions.

- Number of atezolizumab, carboplatin and etoposide infusions (Part 1B).
- (Actual)Treatment Duration (weeks) defined as follows: (Date of last administration - Date of first administration + Planned Duration) / 7, where the Planned Duration (days) is defined as the planned time between two consecutive administrations. In Part 1A, planned duration for BNT411 is one week for the first four cycles, followed by once every 3 weeks. In Part 1B, planned duration for BNT411 for the first four cycles is 6 days if the patients' last dose was the first dose within any cycle, 7 days if the patients' last dose was the second dose within any cycle and 8 days if the patients' last dose was the third dose in within any cycle. After 4 cycles planned duration for BNT411 is 3 weeks. Planned duration for atezolizumab is every 3 weeks, for carboplatin it is 21 days apart till Cycle 4 and for etoposide planned duration is one day till day 3 of the Cycle 4. Actual treatment duration is calculated for each treatment separately.
- Planned Treatment Duration (weeks) defined as (scheduled date of last administration - scheduled date of first administration + Planned Duration) / 7. The scheduled date of last administration is the date at which the last administration should be given according to the CTP schedule. Planned duration is as above.
- (Actual) Cumulative Dose defined as sum of all administered doses for each trial treatment. BNT411 (μg) for Part 1A and Part 1B and atezolizumab (mg), carboplatin (mg), and etoposide (mg) for Part 1B. Calculated for each treatment separately.
- Planned Cumulative Dose defined as sum of all planned doses, separately, for each trial treatment. BNT411 (μg) for Part 1A and Part 1B and atezolizumab (mg), carboplatin (mg), and etoposide (mg) for Part 1B.
- Dose Intensity is defined as Cumulative Dose for that trial treatment (unit for that trial treatment) / (Actual) Treatment Duration (weeks) for that trial treatment.
- RDI % (using units for BNT411) is defined as follows:

$$\text{RDI (\%)} = \frac{\text{Actual Dose Intensity } \left(\frac{\mu\text{g}}{\text{week}} \right)}{\text{Planned Dose Intensity } \left(\frac{\mu\text{g}}{\text{week}} \right)} \times 100 = \text{DI} \times \text{TI} \times 100,$$

Where

$$\text{Actual Dose Intensity } \left(\frac{\mu\text{g}}{\text{week}} \right) = \frac{\text{(Actual) Cumulative Dose } (\mu\text{g})}{\text{(Actual) Treatment Duration (weeks)}}$$

$$\text{Planned Dose Intensity } \left(\frac{\mu\text{g}}{\text{week}} \right) = \frac{\text{Planned Cumulative Dose } (\mu\text{g})}{\text{Planned Treatment Duration (weeks)}}$$

$$\text{Dose Index (DI)} = \frac{\text{Total Administered Dose } (\mu\text{g})}{\text{Total Planned Dose } (\mu\text{g})}$$

$$\text{Time Index (TI)} = \frac{\text{Planned Treatment Duration (weeks)}}{\text{Actual Treatment Duration (weeks)}}$$

The units in the derivations above are for BNT411. For atezolizumab, carboplatin and etoposide the unit is mg.

The following variables will be presented with summary statistics for each trial treatment by cohort for each trial part:

- Number of cycles received (categorical, Cycle 1-2, 3-4, 5-6, 7-8, 9-10, 11-12, 13-14, 15-16, 17-20 21-24 and so on, aligned to the tumor assessments every 6 weeks and 12 weeks respectively)
- Number of BNT411 infusions (descriptive statistics)
- Number of BNT411 infusions (categorical, 1, 2, 3 and so on)
- Number of atezolizumab, carboplatin and etoposide infusions (descriptive statistics) (Part 1B)
- Number of atezolizumab, carboplatin and etoposide infusions (categorical, 1, 2, 3 and so on) (Part 1B)
- Treatment duration
- Cumulative dose
- Dose intensity
- RDI

Additionally, the RDI will be presented categorically (i.e., number and percentage of patients with RDI of <60%, 60-<80%, ≥80%). Moreover, the number and percentage of patients with any dose delay, 4-7 days, > 7 days of dose delay and with any dose modification, dose reduction, dose increase, at least one dose modification and at least two dose modification and any dose interruption will be presented separately for each trial treatment for each trial part. Dose reduction and dose increase will be calculated as planned dose - given dose or total dose.

All the above mentioned dose exposure variables will be presented in a by-patient listing. A by-patient listing of treatment administration will be presented.

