# 6.1.2 Atezolizumab, Carboplatin, and Etoposide

Atezolizumab, carboplatin, and etoposide will be used in the commercially available formulation.

For information on the formulation, packaging, and handling of atezolizumab, carboplatin, and etoposide, see the prescribing information for each drug.

The recommended dosage of atezolizumab is 1200 mg intravenously over 60 minutes every 3 weeks. If the first infusion of atezolizumab is tolerated, all subsequent infusions may be delivered over 30 minutes.

Carboplatin should be administered after completion of atezolizumab by intravenous infusion over 30–60 minutes to achieve an initial target AUC of 5 mg/mL/min (Calvert formula dosing) with standard anti-emetics per local practice guidelines. Because of their immune-suppressive effect, premedication with corticosteroids should be minimized to the extent that is clinically feasible.

On Day 1 of each cycle, etoposide ( $100 \text{ mg/m}^2$ ) should be administered intravenously over 60 minutes following carboplatin administration. The dose will be calculated using the Mosteller formula (BSA [ $m^2$ ] = square root((height [cm] x weight [kg])/3600))

On Day 2 and Day 3 of each cycle, etoposide (100 mg/m²) should be administered intravenously over 60 minutes. Premedication should be administered according to local standard-of-care. Because of their immune-suppressive effect, premedication with corticosteroids should be minimized to the extent that is clinically feasible.

After the DLT-observation period, if the patient tolerates the combination of atezolizumab+carboplatin+etoposide+BNT411, chemotherapy should continue for a total of 4 cycles; further chemotherapy cycles at the investigator's discretion should be discussed with the Medical Monitor. After completion of chemotherapy, atezolizumab+BNT411 combination should continue until one of the protocol-defined treatment discontinuation criteria is met (Section 7.1).

For the dosing schedule, refer to the Schedule of Activities (SoA), Section 1.3.

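### SAP 8.5.1 leaves out the rest period after a Day 3 etoposide dose, so etoposide dose intensity is overstated 1.27- to 7-fold when the last dose falls on Day 3

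*SAP*

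**What the plan says.** SAP 8.5.1 (Extent of exposure) computes actual treatment duration in weeks as "Date of last administration - Date of first administration + Planned Duration) / 7", and states that "Planned Duration (days) is defined as the planned time between two consecutive administrations". Planned treatment duration uses scheduled dates and the same Planned Duration. Dose intensity is cumulative dose over actual duration. RDI is actual over planned dose intensity, which equals a dose index times a time index.

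The section then gives a Planned Duration for each drug:

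- BNT411 in Part 1B, first four cycles: 6 or 7 days after the first or second dose of a cycle, and "8 days if the patients' last dose was the third dose in within any cycle".
- Carboplatin: "for carboplatin it is 21 days apart till Cycle 4".
- Etoposide: "for etoposide planned duration is one day till day 3 of the Cycle 4".

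Protocol 6.1.2 places etoposide on Day 1 of each cycle and again "On Day 2 and Day 3 of each cycle, etoposide". The SAP's trial design table repeats that schedule. RDI is reported as a continuous variable and in three categories: below 60%, 60% to below 80%, and 80% or more. For the DLT evaluation set, the exposure summary uses Cycle 1 only.

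**The concern.** The one-day value fits the gap between Days 1 and 2 and between Days 2 and 3, but not the gap from Day 3 to the next cycle. The same paragraph carries the gap into the next cycle for BNT411 and carboplatin, so etoposide alone loses the rest at the end of its last cycle. The loss is a fixed 18 days, so it matters most in patients with few cycles. A patient who stops after one cycle would appear far more intensively treated than one who completes four on the same schedule. At stake is whether the etoposide dose intensity and RDI figures in the Part 1B exposure tables can be read across patients and BNT411 cohorts.

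**Working it through.** **Inputs.** Etoposide on Days 1, 2 and 3, 100 mg/m² per dose, four cycles recommended (Protocol 6.1.2); 21-day cycle (SAP 3.2); formulas and Planned Durations from SAP 8.5.1.

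**Step 1: reproduce the SAP's gaps from its definition.**

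- BNT411 Part 1B (Days 2, 8, 15): 8 − 2 = 6, 15 − 8 = 7, (2 + 21) − 15 = 8 days. Agrees with the SAP.
- Carboplatin (Day 1): 21 days. Agrees.
- Etoposide (Days 1, 2, 3): 1, 1, and (1 + 21) − 3 = 19 days. The SAP's one day agrees after Days 1 and 2, but not after Day 3.

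**Step 2: dose intensity, on schedule, last dose on Day 3.** With c complete cycles the last dose falls on day 21(c − 1) + 3. Duration is that day − 1 + gap. Cumulative dose is 300c mg/m².

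| Cycles | Days, SAP (gap 1) | Days, definition (gap 19) | mg/m²/week, SAP | mg/m²/week, definition | Ratio |
|---|---|---|---|---|---|
| 1 | 3 | 21 | 300/(3/7) = 700 | 100 | 7.0 |
| 2 | 24 | 42 | 600/(24/7) = 175 | 100 | 1.75 |
| 3 | 45 | 63 | 900/(45/7) = 140 | 100 | 1.40 |
| 4 | 66 | 84 | 1200/(66/7) = 127.3 | 100 | 1.27 |

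The SAP tabulates etoposide in mg, so the mg/m² figures are illustrative; the ratios carry over. In the Cycle-1-only table for the DLT evaluation set, the ratio is 7.0 for every patient with all three doses on schedule. Protocol 6.1.2 allows further cycles after discussion with the Medical Monitor; with six (an assumption) the ratio would be 126/108 = 1.17.

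**Step 3: RDI if the planned figures cover the doses received.** At full dose, RDI = planned/actual duration. With no delay it is 100% under either gap. With a delay:

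| Case | SAP | Gap of 19 days | Category |
|---|---|---|---|
| 4 cycles, 7 days late | 66/73 = 90.4% | 84/91 = 92.3% | same |
| 4 cycles, 14 days late | 66/80 = 82.5% | 84/98 = 85.7% | same |
| 4 cycles, 21 days late | 66/87 = 75.9% | 84/105 = 80.0% | changes |
| 2 cycles, 7 days late | 24/31 = 77.4% | 42/49 = 85.7% | changes |
| Cycle 1 only, Day 3 two days late | 3/5 = 60.0% | 21/23 = 91.3% | changes |

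Over four full-dose cycles the category differs only for total delays of 17–21 or 45–56 days.

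**Step 4: RDI if the planned figures cover all four cycles.** A patient who stops after one full-dose cycle has dose index 3/12.

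- SAP: time index 66/3 = 22, so RDI = 0.25 × 22 = 550%.
- Gap of 19 days: time index 84/21 = 4, so RDI = 0.25 × 4 = 100%.

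If that patient received half of each dose, the values are 275% and 50%, so a patient who belongs below 60% is placed at 80% or more.

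**Step 5: last dose on Day 1 or Day 2.** One day is then the correct gap and the SAP follows its definition. The result can still be extreme: two doses ending on Cycle 1 Day 2 give 200/(2/7) = 700 mg/m²/week.

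**The case against.** Several objections stand in whole or in part.

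- **The error is confined to Day 3.** A reader might infer that the one-day rule is wrong after every dose. It is not: Step 1 shows it is right after Days 1 and 2.
- **The factor does not pass into RDI.** A reader might infer from a 7-fold error in dose intensity that RDI is generally put in the wrong category. The same Planned Duration enters planned and actual duration, so on-schedule patients are unaffected and delays of 7 or 14 days over four cycles leave the category unchanged. Misclassification needs particular delays, or early stopping with reduced doses on the full-course reading. The Cycle 1 example is an edge case: the Part 1B schedule allows Day 3 to be up to two days late, but reserves that window for cases where immune phenotyping makes it unavoidable.
- **Other output shows chemotherapy delivery directly.** SAP 8.5.1 also reports, for each drug, infusions, cycles, cumulative dose, delays, reductions and interruptions, with by-patient listings. Neither document makes etoposide intensity the test of whether BNT411 compromises the chemotherapy.
- **Correcting the gap does not remove every inflated value.** Step 5 stands, which is why the fix includes a flag.

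One defence does not stand: that duration should simply end with the last etoposide dose because no further dose is planned after Cycle 4. Carboplatin also stops at Cycle 4, and the SAP still credits it with 21 days.

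**Conclusion.** The etoposide rule contradicts the SAP's own definition and gives wrong tabulated values. Dose intensity is overstated 7.0-, 1.75-, 1.40- and 1.27-fold for 1, 2, 3 and 4 complete on-schedule cycles. This rests only on the stated schedule and on the last dose being on Day 3.

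The RDI consequence is conditional. The SAP defines the scheduled last administration by reference to the protocol schedule, without saying whether that means the doses received or the whole four-cycle course. On the first reading RDI is too low in delayed patients; on the second it is too high in early stoppers.

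A reader might also infer that DLT evaluability or dose escalation is touched. The documents do not support that: the minimum exposure criterion in SAP 7.1 uses the BNT411 RDI, whose Part 1B gaps are correct, and no hypothesis is tested. The effect is limited to descriptive Part 1B etoposide exposure tables and listings. Severity: minor.

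**What to change.** In SAP 8.5.1:

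1. Set etoposide Planned Duration to 1 day after a Day 1 or Day 2 dose and 19 days after a Day 3 dose, in both actual and planned treatment duration, for as many chemotherapy cycles as are given.
2. State whether planned dose and planned duration cover the cycles started or all four cycles.
3. Flag patients whose last etoposide dose is on Day 1 or Day 2, since their dose intensity stays inflated under the SAP's definition.

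The cost is a few sentences in the SAP, a small change to the derivation code and one footnote. No data collection or treatment rule changes.

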8.5.2 Adverse events

This section includes the description of the analysis planned for the primary endpoints on this trial.

AEs will be coded using the most recent version of Medical Dictionary for Regulatory Activities (MedDRA®) coding system version 26.0 or higher to get a SOC and PT for each AE and graded for severity using NCI CTCAE v5.0. In case a patient has an AE with missing relationship status, the event will be assumed to be related and associated with the treatment received in the summaries (will be listed as collected in the listings). No imputation for missing NCI-CTC grades will be performed.

A treatment-emergent AE (TEAE) is defined as any AE with an onset date on or after the first administration of trial treatment (BNT411 in part1A and BNT411, atezolizumab, carboplatin, and etoposide in Part 1B) (if the AE was absent before the first administration of trial treatment) or worsened after the first administration of trial treatment (if the AE was present before the first administration of trial treatment). AEs with an onset date more than 60 days after the last administration of trial treatment will be considered as treatment-emergent only if assessed as related to trial treatment (BNT411 for Part 1A and BNT411, atezolizumab, carboplatin, and etoposide for Part 1B) by the investigator.

Treatment-emergent AEs will be summarized by cohort and trial part and total within trial part. In addition, treatment-related TEAEs will be summarized by cohort and trial treatment (BNT411, atezolizumab, carboplatin, and etoposide) within trial part.

Only TEAE data will be summarized for the Safety set for each trial part (Part 1A and Part 1B). Non-TEAEs will be listed only.

Dose-limiting toxicities

In general, a DLT for a drug or other treatment is defined as one or more AEs that prevents an increase of the dose level of that treatment (for details on dose escalation decision rules see Appendix 5).

Serious AEs (SAEs), non-serious grade ≥ 3 AEs and clinically significant abnormal laboratory values grade ≥ 3 will be collected and assessed for DLTs (for each dose level during the first cycle). Common Terminology Criteria for Adverse Events (NCI CTCAE) v.5.0 will be used to grade the intensity of AEs.

More details regarding DLTs can be found in the Section 6.6 of the CTP.

For the additional rules and considerations of MTD and RP2D other than what was already defined in Section 1.1, see Section 4.1.1.2 of the CTP.

The number and percentage of patients reporting DLTs will be summarized by PT nested within SOC for each cohort by trial part using the DLT evaluation set.

A separate listing of DLTs will be presented, including reported term, SOC, PT, time of onset, duration, outcome, relationship to trial treatment, NCI CTCAE grade, and seriousness including dose exposure data during the first cycle (i.e., 21 days).

Overall summary of adverse events (AE)

The number and percentage of patients reporting at least one AE will be summarized for each of the following AE types by cohort and trial part (Parts 1A and 1B). Related applies to a separate summary for BNT411 in Part 1A and BNT411, atezolizumab, carboplatin, and etoposide and any NIMP/IMP in Part 1B, unless otherwise specified :

- any TEAE
- related TEAE
- grade ≥ 3 TEAE
- related grade ≥ 3 TEAE

- any treatment-emergent serious AE (TESAE)
- related TESAE
- TESAE leading to death
- Related TESAE leading to death
- TEAEs leading to dose reduction and dose interruption (BNT411 in Part 1A or BNT411, atezolizumab, carboplatin, and etoposide in Part 1B)
- TEAE leading to permanent discontinuation of treatment (BNT411 in Part 1A or BNT411, atezolizumab, carboplatin, and etoposide in Part 1B)
- DLTs

Analyses of adverse events

The number and percentage of patients reporting at least one TEAE will be summarized by PT nested within SOC for each of the above AE categories. If an SOC / PT is reported more than once for a patient, the patient will only be counted once for this SOC / PT. Strongest relationship or worst grade will be counted if a TEAE is reported more than once by the same patient for a SOC / PT. The common TEAE occurring in $\geq 10\%$ of the patients will be summarized separately.

All AE summary tables will be sorted in descending frequency order by SOC and PT within SOC.

Analyses of other adverse events (excluding serious AEs)

The number and percentage of patients reporting other TEAEs (excluding TESAEs) will be summarized by PT nested within SOC. If a SOC / PT is reported more than once for a patient, the patient will only be counted once for this SOC / PT.

All AE summary tables will be sorted in descending frequency order by SOC and PT within SOC.

TEAE by relationship

The number and percentage of patients with TEAEs will be summarized by 'ALL' and 'Related' to trial treatment (BNT411, atezolizumab, carboplatin, and etoposide) by PT nested within SOC. If an AE is reported more than once by the same patient for a SOC / PT the related AE will be counted once for this SOC / PT. The relationship to trial treatment will be counted as related if relationship status is reported as missing for an AE.

TEAE by NCI-CTC grade

The number and percentage of patients with TEAEs will be summarized by worst NCI-CTC grade by PT nested within SOC. Worst grade will be counted if an AE is reported more than once by the same patient for a SOC / PT. The related TEAEs by worst NCI-CTC grade will be summarized separately.

The number and percentage of patients with grade ≥ 3 AEs and related grade ≥ 3 AEs will be summarized by PT nested within SOC. In addition, AEs with a missing grade will be presented in the summary table as a grade category of “Missing.”

Deaths

- All deaths including those that occurred on-treatment (on or after date of first dose of BNT411) and post-treatment, will be listed, post-treatment deaths will be flagged. In addition to the summary of on-treatment deaths an additional summary of all deaths (on-treatment + post-treatment) will be provided along with primary reason for death.
- A separate summary of TESAEs leading to death will be provided by PT nested within SOC.
- A separate summary of related TESAEs leading to death will be provided by PT nested within SOC.

Serious Adverse Events and Other Significant Adverse Events

The number and percentage of patients

- with any TESAE,
- with any related TESAE (separately for each trial treatment and total),
- with any TESAE leading to death,
- with any related TESAE leading to death,
- with any TEAE leading to permanent discontinuation of treatment (BNT411, atezolizumab, carboplatin, and etoposide), or
- with any TEAE leading to dose reduction or interruption

will be summarized by PT nested within SOC by cohort within each trial part.

Deaths

In addition to a summary of on-treatment (on or after date of first dose of BNT411 until...) deaths and primary reason for death an additional summary of all deaths (on-treatment + during follow-up) will be provided along with primary reason for death. by cohort for each trial part. All deaths including those that occurred on-treatment and during follow-up, will be listed, post-treatment deaths will be flagged.

AE listings

All deaths, AEs, SAEs and TEAEs leading to permanent discontinuation of treatment, and discontinuation from trial will be listed. Also a listing of TEAEs leading to death will be provided. DLTs will be flagged in all AE listings. The listings will be sorted by trial part, cohort and patient within cohort.

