# 3 Objectives and Endpoints

Objectives and related endpoints are described in Table 3-1 below.

**Table 3-1:** Objectives and Endpoints

OBJECTIVES	ENDPOINTS		
Primary			
• For Parts 1 and 2: Assess safety profile	Occurrence of DLTs within a patient during the DLT evaluation period		
	• Occurrence of TEAEs within a patient including grade ≥3, serious, fatal TEAE by relationship		
	Occurrence of dose reduction and discontinuation of BNT411 within a patient due to TEAEs		
For Part 1: Determine MTD and/or RP2D	MTD defined as the highest tolerated dose		
	RP2D based on integrated evaluation of safety, tolerability, clinical benefit, PK, and pharmacodynamic data, for all dose levels tested		
Secondary			
• For Parts 1 and 2: Establish PK profile	PK parameters (AUC, CL and V D , C max , T max , C trough , and T 1/2 )		
For Part 2: Evaluate anti-tumor activity according to RECIST 1.1	ORR defined as the proportion of patients in whom a CR or PR is observed as best overall response.		
	DCR defined as the proportion of patients in whom a CR or PR or SD (assessed at least 6 weeks after first dose) is observed as best overall response.		
	DOR defined as the time from first objective response (CR or PR) to the date of the first occurrence of objective tumor progression or death from any cause, whichever occurs first.		

OBJECTIVES	ENDPOINTS		
Exploratory			
For Part 2: Evaluate anti-tumor activity according to iRECIST	• iORR defined as the proportion of patients in whom a iCR or iPR is observed as best overall response.		
	• iDCR defined as the proportion of patients in whom a iCR or iPR or iSD (assessed at least 6 weeks after first dose) is observed as best overall response.		
	• iDOR defined as the time from first objective response (iCR or iPR) to the date of the first occurrence of objective tumor progression (iCPD) or death from any cause, whichever occurs first.		
For Part 2: Evaluate preliminary efficacy	
 
PFS defined as the time from first dose of BNT411 to first occurrence of objective tumor progression (per RECIST 1.1), or death from any cause, whichever occurs first.
 
OS defined as the time from first dose of BNT411 to death from any cause.
 
		

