#### 9.4.2 Primary Endpoint(s)

The primary objective of the trial is to assess the safety profile of the regimen based on the following endpoints:

- Occurrence of dose limiting toxicities (DLTs) within a patient during the DLT evaluation period
- Occurrence of treatment-emergent adverse events (TEAE) within a patient including grade ≥3, serious, fatal TEAE by relationship
- Occurrence of dose reduction and discontinuation of BNT411 within a patient due to treatment-emergent adverse events (TEAE)

And to determine the MTD and/or RP2D defined as follows:

- MTD the highest tolerated dose
- RP2D based on integrated evaluation of safety, tolerability, clinical benefit, PK, and pharmacodynamics data, for all dose levels tested.

A treatment emergent AE is defined as any AE with an onset date on or after the first administration of trial treatment (if the AE was absent before the first administration of trial treatment) or worsened after the first administration of trial treatment (if the AE was present before the first administration of trial treatment). AEs with an onset date more than 60 days after the last administration of trial treatment will be considered as treatment emergent only if assessed as related to trial treatment by the investigator. Treatment-emergent AEs will be summarized overall and by treatment arm. The trial treatment includes BNT411, atezolizumab, carboplatin, and etoposide.

AEs will be coded using the most recent version of Medical Dictionary for Regulatory Activities (MedDRA®) coding system to get a System Organ Class (SOC) and Preferred Term (PT) for each AE and graded for severity using NCI CTCAE v5.0.

The number and percentage of patients reporting at least one AE will be summarized by PT nested within SOC for each of the following AE types:

- any AE
- related AE
- Grade >3 AE
- related Grade ≥3 AE
- any SAE
- related SAE
- SAE leading to death
- AE leading to dose reduction
- AE leading to permanent discontinuation of treatment
- DLT.

Moreover, the number and percentage of patients with any AE will be summarized by worst NCI CTCAE grade by PT nested within SOC.

DLTs will be presented in terms of listings presenting the reported term and MedDRA PT and SOC term, its time of onset, duration, and outcome, relationship, NCI CTCAE grade, and seriousness including dose exposure data.

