## Action taken by the investigator to trial treatment

Action(s) taken by the investigator as a result of an AE must be documented.

Action(s) taken with trial treatment by the investigator can be:

- Dose not changed (= continuation of trial treatment administration according to the trial protocol)
- Dose reduced
- Trial treatment withdrawn temporarily (= interruption and resumption):
  - Delayed start of the next vaccination
  - o Cancellation of administration at a given visit
  - o Interruption of trial treatment administration during a given visit
- Trial treatment permanently withdrawn (= discontinuation)
- Unknown (e.g., in case the subject is lost to follow-up)
- Not applicable (e.g., in case treatment with trial treatment has not yet started or event starts after last trial treatment administration)

Other action(s) that may be taken by the investigator include:

- None
- Initiation of a concomitant drug therapy for the treatment of the AE
- Termination of a concomitant drug therapy (please specify; e.g. if this might be the cause of the AE)
- Change of the dose of a concomitant medication
- Hospitalization or prolongation of hospitalization (please complete SAE-Form)
- Initiation/termination of a non-drug therapy
- Other (please specify)

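### SAP 8.5.2 merges TEAE-caused dose reduction with interruption, so the BNT411 dose-reduction half of a primary safety endpoint has no result of its own

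*SAP*

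**What the plan says.** Protocol Table 3-1 lists as a primary endpoint "Occurrence of dose reduction and discontinuation of BNT411 within a patient due to TEAEs". Protocol 9.4.2 and SAP Table 2 repeat it. It covers two actions, reduction and discontinuation, and one drug, BNT411.

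Among the tables planned in Protocol 9.4.2 are "AE leading to dose reduction" and, as a separate item, "AE leading to permanent discontinuation of treatment". Interruption is not in that list.

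SAP 8.5.2 states that it holds the analysis of the primary endpoints. Its overall summary has a line for "TEAEs leading to dose reduction and dose interruption (BNT411 in Part 1A or BNT411, atezolizumab, carboplatin, and etoposide in Part 1B"), followed by a separate line for permanent discontinuation with the same drug list. The later list of serious and other significant events has "with any TEAE leading to dose reduction or interruption", again with discontinuation apart.

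SAP 8.5.1 counts delay, reduction and interruption for each drug as exposure variables, and states: "Dose reduction and dose increase will be calculated as planned dose - given dose or total dose".

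The action-taken list in Protocol 10.3.3 keeps a reduced dose apart from "Trial treatment withdrawn temporarily (= interruption and resumption"). The latter category includes a delayed start, a cancelled administration and a pause during a visit.

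SAP Appendix 1 lists two changes from the protocol's analyses: the enrolled set, and the restriction of summaries to TEAEs.

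**The concern.** A reduction and an interruption are different events. Protocol 6.6.3.1 and 6.6.3.2 allow BNT411 to resume at the same level or at a lower one after a delay, so a delay need not lead to a reduction. Protocol 6.6.4.2 has the infusion interrupted for a Grade 2 or 3 infusion-related reaction, with a possible restart. If such a pause enters the same row as a move to a lower dose level, the row no longer measures what the endpoint names.

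This matters because the row stands in for half of a stated primary endpoint. Protocol 4.1.1.2 also asks that toxicities other than DLTs be weighed in choosing the RP2D. A reader of the report who looks for TEAE-caused BNT411 reductions would find a broader count and no means in the table of separating it.

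**Working it through.** No test, power or sample-size figure is involved, so the check compares the endpoint with each output that could deliver it.

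**1. Coverage in SAP 8.5.2**

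| Endpoint component | Part 1A | Part 1B |
|---|---|---|
| BNT411 reduction due to TEAE | Only together with interruption; BNT411 is the only drug | Only together with interruption; four drugs named, split not stated |
| BNT411 discontinuation due to TEAE | Own line, BNT411 only | Own line; four drugs named, split not stated |

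The overall-summary categories are then repeated by SOC and PT, so the combined category carries through to those tables.

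**2. One row or two.** The overall summary joins the terms with *and*, which could mean two outputs. The second list joins them with *or*, which is a single category.

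**3. What interruption covers.** SAP 8.5.2 does not define it. The only description in the documents is the action-taken list in Protocol 10.3.3, which puts delay, cancellation and an in-visit pause under interruption. If the SAP follows that list, a TEAE-caused delay or pause is counted with a reduction. SAP 8.5.1 treats delay and interruption as separate variables, so this reading is plausible but not settled.

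**4. Other outputs**
- SAP 8.5.1 separates the actions by drug but does not tie them to TEAEs. Reduction there is a difference between planned and given dose, so a part-given infusion would count whatever its cause.
- SAP 8.2 gives discontinuation from each drug with the primary reason. This supports the discontinuation component and says nothing about reduction.
- The AE listings in SAP 8.5.2 single out discontinuation and death, but not reduction.

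**5. Size.** SAP 8.1 bases AE percentages on the N of the analysis set. Each patient with an interruption but no reduction therefore adds 100/N percentage points to the row:
- N = 3: 100/3 = 33
- N = 6: 100/6 = 17
- N = 14 (the backfill ceiling in Protocol 4.1.1.1): 100/14 = 7

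The documents give no rate of TEAE-caused interruption. As an assumption, take a cohort of six with one BNT411 reduction and k other patients with an interruption only. The endpoint value is 1/6 = 17%. The combined row is (1 + k)/6:

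| k | 0 | 1 | 2 | 3 | 4 | 5 |
|---|---|---|---|---|---|---|
| Combined row | 17% | 33% | 50% | 67% | 83% | 100% |

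These values show the possible range. They are not a forecast.

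**The case against.** The strongest reply is that most of the information is still there. Discontinuation has its own line in both lists, is BNT411-only in Part 1A, and is backed by the per-drug disposition table and a listing. SAP 8.5 lists all safety data, cohorts are small, no hypothesis is tested, and the escalation rules do not use this row. All of this stands and limits the consequence. It does not supply the missing reduction result.

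Three stronger readings are tempting, and the documents do not support them.

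- *The primary endpoint is not produced at all.* The discontinuation component is produced in Part 1A, and a TEAE discontinuation line exists in Part 1B. This is also one of several primary safety endpoints.
- *Any dose delay counts as a reduction.* Only actions caused by a TEAE enter these tables, so a delay for cranial irradiation or logistics does not. A TEAE-caused delay enters only if interruption follows the protocol's action-taken list.
- *In Part 1B a carboplatin delay or an etoposide stop counts toward the BNT411 endpoint.* The SAP names four drugs but does not say they are pooled. SAP 8.5 allows summaries by treatment where appropriate, and SAP Appendix 3 sets separate Part 1B display codes for each drug. Protocol 9.4.2 does not limit its own tables to BNT411 either, so the mismatch in drug scope begins in the protocol. What remains is an ambiguity: the SAP states a per-drug split for related events but not for these lines.

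Nor can it be said that comparison between the parts is lost. SAP 8.1 plans no formal comparison between them, and they already differ in population and background treatment.

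**Conclusion.** The point holds for the reduction component. SAP 8.5.2, followed as written, reports a broader event in place of TEAE-caused BNT411 dose reduction in both parts. No other output supplies that result, and the departure from Protocol 9.4.2 is undeclared. For discontinuation, the only gap is that Part 1B does not state a per-drug split.

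The merging rests on the wording of the second list in SAP 8.5.2; the first list alone would be ambiguous. That delays and infusion pauses fall inside the merged row rests on the assumption that interruption follows Protocol 10.3.3. The numerical effect is unknown: 33 points per reclassified patient at N = 3, 17 at N = 6 and 7 at N = 14. This should be corrected before the report tables are produced. It does not undermine the escalation decisions.

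**What to change.** In both lists of SAP 8.5.2, replace the combined line with separate rows:

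- TEAE leading to BNT411 dose reduction, labelled as primary endpoint
- TEAE leading to permanent BNT411 discontinuation, labelled as primary endpoint
- TEAE leading to BNT411 interruption or delay

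In Part 1B, show the same rows for atezolizumab, carboplatin and etoposide, each drug separately.

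Define interruption against the action-taken categories in Protocol 10.3.3. Derive reduction from the dose-reduced category for BNT411, not from planned minus given dose. Record any departure that is kept in SAP Appendix 1.

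The cost is SAP wording and a few table rows. One item needs checking first. Protocol 10.3.3 records action taken with trial treatment, and Protocol 6.1 lets that term mean any of the four drugs, so per-drug capture in Part 1B cannot be confirmed from the documents. If it is not captured per drug, each AE would have to be linked to the BNT411 administration record. That is extra programming and review, but it needs no new patient data.
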